# Impact

This study will evaluate the impact of the VD-HCBS program and provide key insights into the implementation and effectiveness of this program. This evaluation may provide insight to VA policymakers and VA care providers that helps them ensure that community based LTSS options are adequately administered and help refine policies regarding the mission and operations of VD-HCBS to align with VHA and GEC goals. List of Abbreviations

ACL -- Administration for Community Living

ADNAs -- Aging and Disability Network Agencies

BIC -- Bayesian Information Criterion

CCDE -- Cash and Counseling Demonstration and Evaluation

CDW -- Corporate Data Warehouse

CFIR -- Consolidated Framework for Implementation Research

CITI -- Collaborative IRB Training Initiative

COIN -- Centers of Innovation

CREATE -- Collaborative Research to Enhance and Advance Transformation and Excellence Initiative

ERIC -- Expert Recommendations for Implementing Change

FMS -- Financial Management Service

GEC -- Office of Geriatrics and Extended Care

GLMMs -- Generalized Linear Mixed Models

HSR&D/QUERI -- Health Services Research & Development/Quality Enhancement Research Initiative

IIR -- Investigator Initiated Research

IRB -- Institutional Review Board

LTC -- Long-Term Care

LTSS -- Long-Term Services and Supports

NRCPDS -- National Resource Center for Participant-Directed Services

OIG -- Office of Inspector General

P1a -- High Priority Veteran

PCAFC -- Program of Comprehensive Assistance for Family Caregivers

PEPReC -- Program Evidenced-based Policy Resource Center

QCA -- Qualitative Comparative Analysis

QUAN+QUAL -- Quantitative/Qualitative

SCI -- Spinal Cord Injury

TBI -- Traumatic Brain Injury

USH -- Undersecretary for Health

VA-CARES -- VA Caregiver Evaluation Center

VAMCs -- VA Medical Centers

VD-HCBS -- Veteran-Directed Home and Community Based Services

VHA -- Veterans Health Administration

VINCI -- VA Informatics and Computing Infrastructure

VPN -- Virtual Private Network

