## 2.0 Introduction

In the next decade, the number of older high priority (P1a) Veterans will double. The VA has a statutory obligation to purchase or provide institutional care to all P1a Veterans. At a cost of \$110,000 per Veteran per year for institutional care, the ability of the VA system to honor its statutory obligations will be challenged with current resources. As stated by the 2013 Office of the Inspector General report,  there is a rapid need to rebalance the focus from institutional programs to non-institutional programs. In FY14, VA's Office of Geriatrics and Extended Care (GEC) spent 74% of its budget on institutional care and 26% on non-institutional long-term services and supports (LTSS). For comparison, state Medicaid programs, which are under a statutory obligation to provide institutional care, devote the majority (51%) of LTSS spending to non-institutional care. In an effort to meet this impending demand, GEC has been working toward developing a dynamic system of LTSS that shifts the delivery of long-term care (LTC) from institutions to the community.

As part of this rebalancing plan, GEC has implemented many innovative programs to postpone or prevent institutionalization. Recognizing the need to increase home and community-based services (HCBS) utilization for high-need Veterans and following the reported success of the Cash and Counseling Demonstration and Evaluation (CCDE), GEC leadership implemented a

program for Veterans to self-direct their care thereby enabling them to maintain community residence and avoid institutionalization: Veteran-Directed Home and Community Based Services (VD-HCBS). In 2008, a partnership was formed between VA and the Administration for Community Living (ACL) to implement the VD-HCBS program, capitalizing on the home care service delivery experience and skills of ACL's Aging and Disability Network Agencies (ADNAs) and the VHA's commitment and resources. Through this partnership, VAMCs purchase VD-HCBS care management from ADNAs on behalf of Veterans. GEC is planning an expansion of VD-HCBS to an additional 90 VA sites over the next 3 years.

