#### SIGNIFICANCE

**Knowledge to be gained.** Proponents of VD-HCBS suggest that expansion of this program could be one promising solution to meet the increased need for LTSS while containing costs and promoting Veteran-centered care. In addition, it provides an innovative approach to HCBS delivery to Veterans living in rural areas or far from VAMCs. Several VAMCs have documented the success of their programs both in terms of Veterans' satisfaction and reduced NH utilization,  However, uptake of the program varies greatly across the country: only 51 VAMCs offer VD-HCBS and the numbers of Veterans enrolled at each site range from one to 100+. There has been no formal evaluation of implementation or effectiveness of the program and therefore the evaluation we are proposing is significant because it will be the first major evaluation of the effect and implementation of the VD-HCBS program.

**Impact on Veterans and the VA.** Veterans enrolled in VD-HCBS represent a vulnerable population, with most having functional or cognitive deficits, needing >20 hours of home care, and meeting eligibility for long term care. At a cost of \$110,000 per Veteran per year for long-

Version 04/23/2018

term care and a doubling of the number of Veterans eligible for VA-paid long-term care, GECs and Veterans have a mutual interest in preserving Veteran independence in the community. As a result, VD-HCBS has tremendous opportunity to improve the fiscal outlook of GEC's LTSS while delivering the highest level of Veteran-centered care. This proposed VD-HCBS evaluation leverages the utilization analysis of PEPReC, by systematically capturing perspectives of Veterans and Caregivers to provide a comprehensive view of the value of VD-HCBS to all stakeholders.

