## Recruitment Methods:

All quantitative data will be obtained from the data owners (VHA Office of GEC), following an approved Data Use Agreement in accordance with VHA policy. As

part of standard operations, the ADNA meets with the Veteran initially and every 90 days thereafter. During these meetings it is customary for the ADNA to ask about current services, as well as, unmet needs and satisfaction with the program.

The VD-HCBS program currently enrolls ~825 new Veterans annually at existing sites. At newly opened sites, there is a period between readiness review and enrolling Veterans that delays early recruitment. As a result, we anticipate that ~825 Veterans among the new sites will be enrolled annually. With 4 routine ADNA assessments per Veteran, we expect to receive up to 6,600 surveys.

A total of 64 respondents consisting of Veterans or Caregivers will be recruited for qualitative portion of this objective. Recruitment packets will initially be sent using via US Mail to the Veterans' listed residences in the ADNA assessment data or should the addresses not be listed, by using the listed SSN in the ADNA assessment data to access the national Electronic Health Record (EHR) by way of CAPRI/VistAWeb and/or JLV. We will randomly select four Veterans enrolled in VD-HCBS from each of the 16 VAMCs chosen for the implementation analysis described in Objective 3. Veteran selection will be done by inputting all case numbers at a VAMC into a random number generator. This packet will include an introduction letter, refusal postcard, and the CIRB approved information consent sheet. The letter will inform potential participants about the interview, the goal of the interviews, that the interviews will be recorded for transcription purposes and will provide contact information for a Providence-based project staff member to address any questions or concerns they may have prior to participating. They may also use this telephone number to indicate their refusal to participate.

The CIRB approved information consent sheet for Veterans to keep, will describe the procedures and risks and contain contact information should they have any questions.

Also included will be the refusal to participate postcard. Veterans will be asked to complete and return this postcard if they do not wish to participate in the study. Receipt of this postcard by the project staff will terminate all future contact with the Veteran regarding this project.

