## 7.0 Data Analysis

#### **Objective 1:**

Quantitative Analysis of Veteran Survey Data - We will analyze the quantitative data from the Veteran Assessment survey data by calculating descriptive statistics and means for the survey items. We will compare the responses at baseline to responses at 3 months, and to responses at 12 months to gauge early and long-term change in the various domains. We will also calculate differences in change by Veteran characteristics, including care arrangement, functional impairment, socioeconomics, and demographics. This descriptive pre-post analysis will provide a first look at the impact of the VD-HCBS program on Veterans. Lastly, we will use finite mixture models to identify subgroups of Veterans that have similar trends in outcomes. Finite mixture models are clustering methods based upon a statistical model with stochastic elements. Formally, they can be written as  $p(Y_i) =$  $\sum_{i=1}^{J} \pi_i F(Y|G_i = j)$ , where Yi is a vector of outcomes for Veteran i,  $\pi_j$  is the proportion of subgroups j among Veterans, Gi is an unknown group classification for Veteran i, F is the distribution of the outcome at the that subpopulation, and J are the number of subpopulations. We will examine different possible values for the number of subgroups, and select the number with the highest Bayesian Information Criterion (BIC). Our initial model for F will be multivariate Gaussian distribution, which may require appropriate transformations of some of the outcomes (e.g., log). If the Gaussian model will not provide a good fit for the data, we will examine other possible models such as a mixture of t distributions, or a mixture of skewed-Normal distributions. After the model identifies the possible subgroups, we will attempt to describe them by examining the trends in the observed outcomes (e.g., Veterans with increasing outcome trends overall, patients with moderately increasing outcomes at 3 weeks but stable at 12 months). These subgroups will enable us to identify the possible patterns that exist among Veterans exposed to the VD-HCBS program. Following this identification, we will examine qualitative (see below) or quantitative variables that are possibly associated with these patterns, so that we could provide further understanding on the possible effectiveness of the program.

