Because the matching is not exact, there might be minor imbalances between the covariates among Caregivers in VD-HCBS and the control group. To address these minor imbalances, we will rely on general linear regression models to estimate differences in the outcomes between Caregivers who are participating in the VD-HCBS program and those who were part of the VA-CARES evaluation. For continuous outcomes, we will use multiple linear regression  $Y_i = X_i\beta + \tau C_i + \varepsilon_i$ , where Yi is the outcome for Caregiver i, Xi are the covariates, Ci is an indicator variable for Control/VD-HDBS,  $\tau$  is the treatment effect and  $\varepsilon_i \sim N(0, \sigma^2)$ . For the ordinal variable, we will use the proportional odds model  $logit(Y_i < j) = \alpha_j + X_i\beta + \tau C_i$ , where  $\alpha_j$  is the log-odds of the outcome variable j, and the rest of the variables are as previously described. To obtain interval estimates we will use either the variance estimates provided by Abadie & Imbens or the bootstrap procedure.

Dependent Variables – We will examine Caregivers' perceived financial strain, CESD-10 score (screener for depressive symptoms), burden, self-reported health, and positive aspects of caregiving as described in the table below.

Dependent Variables for Objective 2								
Measures of	Measurement							

Independent Variables-To examine improvements in the various outcomes, the models will examine Veteran and Caregiver characteristics that may be related to improvement as well as their baseline values on each of the measures of interest. Most of these characteristics will be measured during baseline surveys of

Item Impact on Finances subscale from the Caregiver Reaction								
Assessment								
es range 3-15 where higher scores indicate higher strain.								
enter for Epidemiologic Studies Depression 10 item Scale (CE SD 10).								
cores range 0-30 where higher scores indicate more depressive								
ymptoms.								
arlt Caregiver Burden. Defined as the level of stress felt by a								
Caregiver. The scale covers the areas most often mentioned by								
Caregivers as problems, including health, psychological well-being,								
nances, social life, and the relationship shared by the Caregiver and								
are recipient.								
cores range 0-48 where higher scores indicate higher burden.								
ingle item from the Health and Retirement Study (2012)								

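### Section 7.0 leaves site out of every Objective 1 and 2 analysis, so uncertainty about Veteran change would be understated if change varies by site, and some characteristic contrasts would mix in site differences

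*Combined protocol and SAP*

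**What the plan says.** Section 7.0, Objective 1 plans means and descriptive statistics, then change over time: "We will compare the responses at baseline to responses at 3 months, and to responses at 12 months to gauge early and long-term change". It goes on: "We will also calculate differences in change by Veteran characteristics, including care arrangement, functional impairment, socioeconomics, and demographics". It then fits a finite mixture in which each Veteran contributes one vector of outcomes. Repeated measures within a Veteran are therefore allowed for, but site is not. The section calls the pre-post work descriptive and names no interval, standard error or test.

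For Objective 2, Section 7.0 says: "For continuous outcomes, we will use multiple linear regression", with independent normal errors, and a proportional odds model for the ordinal outcome. Intervals come from a matching-estimator variance or a bootstrap, neither described as clustered. The listed covariates are Veteran and Caregiver characteristics; site is not among them.

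On the structure of the data, the Significance section reports "only 51 VAMCs offer VD-HCBS" and that "the numbers of Veterans enrolled at each site range from one to 100" or more. The program description in Section 2.0 has the ADNA develop the plan of care, monitor services and counsel the Veteran. Section 5.0, Objective 1 (Recruitment Methods) has the same agency visit at the start and every 90 days and ask about services, unmet needs and satisfaction.

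Objective 3c (Section 5.0) examines how implementation strategies and context relate to outcomes. The Qualitative Comparative Analysis in Section 7.0 takes unmet need and satisfaction from Objective 1 for that purpose.

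**The concern.** Objective 3 rests on the premise that site matters for Veteran outcomes, while the Objective 1 analysis of those outcomes proceeds as if it did not. Veterans at one site share a program, and the agency delivering it also records their answers, so their changes may resemble one another. Two consequences follow.

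First, a standard error for mean change that treats Veterans as independent is too small if change varies by site. Section 3.0 says the study will test impact, and the Specific Objectives state that Veterans will improve. Judging that hypothesis needs a measure of uncertainty even though Section 7.0 does not specify one.

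Second, where the prevalence of a characteristic differs between sites, an unadjusted contrast combines the difference within sites with the difference between the sites where those Veterans are served. A gap between strong and weak sites could then be reported as a gap between kinds of Veteran. This affects the point estimate, so it matters whether or not an interval is reported. In the same way, mixture classes could be partly groups of sites.

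**Working it through.** **Inputs from the documents.** Existing sites: 51 (Significance). New sites: 90 (Section 2.0: "GEC is planning an expansion of VD-HCBS to an additional 90 VA sites over the next 3 years"), so up to 51 + 90 = 141. Enrolment: "The VD-HCBS program currently enrolls ~825 new Veterans annually at existing sites", with about 825 more a year expected at new sites, so 1,650. Four assessments per Veteran. Objective 2 power: SD 10, 55 controls, 500 to 2,000 VD-HCBS Caregivers.

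**Assumptions.** The documents give no ICC, no site-size distribution and no alpha. I take an ICC of change of 0.01 to 0.10, a coefficient of variation (CV) of site size of 0 to 1.0, and two-sided alpha 0.05 (which reproduces the power table). The ICC must be that of *change*: a constant site difference in level cancels between baseline and follow-up.

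**Step 1: the plan's own figures.** Surveys: (825 + 825) × 4 = 6,600, as stated. Power for 4 points with 1,000 Caregivers: SE = 10 × √(1/55 + 1/1,000) = 1.385; Φ(4/1.385 − 1.96) = 82.3%, stated 82%. All 12 cells of the table reproduce within one point, so it was computed for independent observations with no design effect. Objective 1 has no power figure.

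**Step 2: mean change in Objective 1.** With mean site size m:

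- DEFF = 1 + ((1 + CV²)m − 1) × ICC
- SE ratio (true to naive) = √DEFF
- effective N = N/DEFF
- coverage of a nominal 95% interval = 2Φ(1.96/√DEFF) − 1

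| Veterans / sites (m) | CV | ICC | DEFF | SE ratio | Effective N | Coverage |
|---|---|---|---|---|---|---|
| 1,650 / 141 (11.7) | 0 | 0.01 | 1.11 | 1.05 | 1,490 | 93.8% |
| 1,650 / 141 | 0 | 0.05 | 1.54 | 1.24 | 1,075 | 88.6% |
| 1,650 / 141 | 1.0 | 0.05 | 2.12 | 1.46 | 778 | 82.2% |
| 1,650 / 141 | 1.0 | 0.10 | 3.24 | 1.80 | 509 | 72.4% |
| 825 / 51 (16.2) | 0 | 0.01 | 1.15 | 1.07 | 716 | 93.2% |
| 825 / 51 | 0 | 0.05 | 1.76 | 1.33 | 469 | 86.1% |
| 825 / 51 | 1.0 | 0.05 | 2.57 | 1.60 | 321 | 77.9% |
| 825 / 51 | 1.0 | 0.10 | 4.14 | 2.03 | 200 | 66.5% |

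Example, 51 sites, CV 1.0, ICC 0.05: 1 + (2 × 16.2 − 1) × 0.05 = 2.57, and √2.57 = 1.60.

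**Step 3: contrasts by characteristic.** Simulation: 51 sites with lognormal sizes (mean about 16, capped at 110), total SD 1, no true within-site effect, nominal 5% two-sample test, 2,000 repetitions. Rejection rates:

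| How the characteristic is spread | ICC 0.02 | ICC 0.05 | ICC 0.10 |
|---|---|---|---|
| Evenly within sites | 5.1% | 4.6% | 5.3% |
| Prevalence varies by site, unrelated to site effect | 7.7% | 10.2% | 14.1% |
| Constant within a site | 11.5% | 20.1% | 31.6% |
| Prevalence tracks the site effect | 34.6% | 66.9% | 88.8% |

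In the last row the contrast is also biased, by 0.11, 0.18 and 0.25 SD.

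**Step 4: Objective 2.** With clustering on the VD-HCBS side only and 1,000 Caregivers, SE ratio = √(100/55 + 0.1 × DEFF) / √(100/55 + 0.1), where 0.1 = 100/1,000.

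- Design effects of 1.30 to 3.97 arise from 1 + (30.7 − 1) × ICC, where 30.7 is the size-weighted mean size in simulated skewed sites (1,650 Veterans, 141 sites). They give 1.396/1.385 = 1.008 and 1.488/1.385 = 1.075.
- The Step 2 formula applied to 1,000 Caregivers in 51 or 141 sites gives ratios of 1.002 to 1.095, and power for 4 points of 82.2% down to 75.1%. At ICC 0.05 and CV 1.0, power is 81.0% with 141 sites or 78.6% with 51.

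The effect is small because the control term, 100/55 = 1.82, dwarfs the VD-HCBS term of 0.1.

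**The case against.** **The analysis is descriptive.** A reader might infer that the plan's Objective 1 intervals are too narrow. It specifies none, so the claim can only be conditional. That correction stands. It does not dispose of the point, because the protocol sets out to test impact and a contrast that mixes in site differences needs no interval to mislead.

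**The sites may be the target, not a sample.** The data come from national program operations. If the aim is only mean change among Veterans at these sites, between-site variance does not enter its error. This has force, and the plan should state its target. But the Abstract wants the findings to inform policy and Section 3.0 speaks of future dissemination. That reaches beyond the Veterans surveyed.

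**The size is assumed.** This stands. The range of one to 100+ is current enrolment at existing sites, not size in the analysis set. Equal sites or a small ICC of change make the problem mild.

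**One agency at every site, also questioning Caregivers.** A reader might infer both. The first is suggested only by the pairing of coordinators in Objective 3; no section says every site has one ADNA. The second is wrong: Caregivers answer a separate telephone survey entered in the project database.

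**Mixed models may be planned elsewhere.** The abbreviation list has "GLMMs -- Generalized Linear Mixed Models", and the references include a stepped-wedge design paper. Neither is used in the text supplied, but part of the protocol before the Data Use Agreements was not available, so the abbreviation proves nothing. What can be said is that Section 7.0 as supplied contains no such model.

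**Within-site contrasts are a preference.** An overall contrast is a legitimate descriptive quantity, and a one-Veteran site adds nothing within site. Both should be shown.

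**Conclusion.** The point holds in conditional form. Section 7.0 as supplied takes no account of site in Objectives 1 and 2, although Objective 3 relates the Objective 1 outcomes to site factors. An interval or test for Veteran change that assumes independence would be too narrow if change varies by site. Under the assumed ICC and CV ranges, the understatement of the standard error runs from about 5% to a factor of two, with 82% or 78% coverage in the middle case. These figures illustrate a range. They are not estimates for this study, since the documents supply neither the ICC nor the site sizes.

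For contrasts, the problem is confined to characteristics whose prevalence varies between sites. Those spread evenly within sites are little affected. The large biases in Step 3 require prevalence to follow the site effect, which the documents neither show nor rule out.

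A reader might infer that Objective 2 is seriously compromised as well. It is not: its standard error rises by roughly 1% to 8% under the first set of design effects in Step 4, and by at most about 10% under the second.

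**What to change.** In Section 7.0, Objective 1:

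- State whether inference is to the Veterans at these sites or to the program more widely.
- Report change from baseline to 3 and 12 months with standard errors clustered by site, or from a mixed model with Veteran and site random effects. If all time points are modelled, the site effect must be allowed on change and not only on level.
- Report the between-site variance of change.
- Show each characteristic contrast twice: overall and adjusted for site.
- Tabulate the mixture classes by site before interpreting them as kinds of Veteran.

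In Objective 2, cluster the variance by site on the VD-HCBS side, or resample that side by site in the bootstrap.

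The cost is modest extra analysis code and wider intervals. No new data should be needed: Veterans are already drawn for interview by VAMC and the Objective 1 outcomes feed a site-level analysis, so site must be identifiable.

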# **5.0 Study Procedures**

## Objective 1 –

The purpose of Objective 1 is to understand the impact of the VD-HCBS program on similar outcomes for Veterans using a mixed qualitative and quantitative method design. The quantitative methodology (Objective 1a) will be a secondary data analysis of the ADNA assessments. These data will be obtained via a Data Use Agreement (DUA) with the VHA Office of Geriatrics and Extended Care. These assessments contain surveys that are administered at each Veteran's initial in-home visit, and quarterly thereafter as part of the national roll-out and operation of the VD-HCBS program. PHI is included in this data set including name, social security number, and date of birth., address, phone number, email (if available), and caregiver contact information. All secondary survey data will be stored on the restricted access Providence VA research server, in a restricted folder in accordance with VA policy.

For the qualitative aim (Objective 1b), we will be conducting semi-structured telephone interviews with a random sample of Veterans (n=64) newly enrolled to VD HCBS (to include the sites involved in the roll out and all other sites with VD HCBS) to gain further insight into the ways in which the VD-HCBS program has impacted their lives. Veterans will be interviewed at two time points in 12 months after initiation of VD-HCBS, for a total of 128 interviews. If a Veteran is unable to communicate on the telephone, we will instead contact their caregiver and invite them to share their own experiences with the program. These interviews will be recorded for transcription purposes. Participants will be sent an information consent sheet, however consent for the interviews and the recording will be acquired verbally as detailed in the interviews will be coded as described in the data analysis section.

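### Objective 1 measures average change with descriptive means but has no plan for Veterans who leave, does not say whether change is paired, and specifies no repeated-measures model.

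*Combined protocol and SAP*

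**What the plan says.** Section 5.0 (Objective 1) describes the Veteran assessments as "administered at each Veteran's initial in-home visit, and quarterly thereafter". Section 7.0 (Objective 1) analyses them by "calculating descriptive statistics and means for the survey items" and continues: "We will compare the responses at baseline to responses at 3 months, and to responses at 12 months". It adds "We will also calculate differences in change by Veteran characteristics, including care arrangement, functional impairment, socioeconomics, and demographics" and characterises the whole as follows: "This descriptive pre-post analysis will provide a first look at the impact of the VD-HCBS program on Veterans".

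The same section then plans finite mixture models on a vector of outcomes per Veteran, initially multivariate Gaussian, to find groups with similar trends. It does not list the waves in that vector or say what happens when some are missing.

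Section 3.0 states a directional hypothesis for Objective 1: outcomes improve relative to before participation. No comparison group is described for this objective.

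Missing data are treated in section 7.0 only under Objective 2, for Caregivers. That text foresees Veterans leaving the program. It plans a baseline comparison of completers with non-completers, multiple imputation and, if needed, a pattern-mixture sensitivity analysis.

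**The concern.** The protocol's Significance section says "Veterans enrolled in VD-HCBS represent a vulnerable population", most with functional or cognitive deficits and eligible for long-term care. Some loss over 12 months through death, institutional care or disenrolment is to be expected. If Veterans who leave had worse scores than those who stay, the mean among 12-month respondents exceeds the mean among all who enrolled, even if nobody changed.

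Without a comparison group, nothing in the Objective 1 analysis would reveal this. The artefact also runs in the direction that the hypothesis predicts. The label of descriptive analysis helps little, because the results are to be read as evidence of impact. Unmet need and satisfaction from Objective 1 also feed the Qualitative Comparative Analysis under Objective 3, so who remains to respond may matter there too.

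**Working it through.** **The plan's own figure.** Section 5.0 expects about 825 new Veterans a year at existing sites and about 825 at new sites, with 4 assessments each: (825 + 825) × 4 = 1,650 × 4 = 6,600. This reproduces the stated ceiling exactly. It is reached only if every Veteran supplies all four. An initial visit plus quarterly visits through 12 months would be five, or 1,650 × 5 = 8,250. If the four include the initial visit, the last falls at 9 months. No attrition rate, SD, alpha or effect size is given for Objective 1, so everything below is illustration on assumed values, with outcomes scored so that higher is better.

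**Unpaired means, general form.** Let p be the share lost, S the stayers' baseline mean and L the leavers'. The baseline mean is (1 − p)S + pL. With no true change the 12-month mean is S. Apparent change = S − [(1 − p)S + pL] = p(S − L).

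- 15% lost, gap 0.3 SD: 0.15 × 0.3 = 0.045 SD
- 25% lost, gap 0.5 SD: 0.25 × 0.5 = 0.125 SD
- 35% lost, gap 0.5 SD: 0.35 × 0.5 = 0.175 SD

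**Unpaired means, loss driven by a frail subgroup.** Let f be the frail share, d its deficit, and l_f and l_n the quarterly loss among frail and other Veterans. The frail share at 12 months is f12 = f(1 − l_f)^4 / [f(1 − l_f)^4 + (1 − f)(1 − l_n)^4], and apparent change = d(f − f12).

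- f = 0.3, d = 0.5 SD, losses 8% and 3%: 83.5% retained, f12 = 0.258, change +0.021 SD
- f = 0.5, d = 1.0 SD, losses 15% and 5%: 66.8% retained, f12 = 0.391, change +0.109 SD
- equal losses in both groups: change 0

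In the second case the implied stayer–leaver gap is 0.109 / 0.332 = 0.33 SD. The upper end of the general range therefore needs stronger selection than a frail subgroup of this kind produces.

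**Paired change.** In both settings above, pairing within Veteran gives exactly 0, because each stayer is compared with himself or herself.

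**Simulation with zero true change.** 1,650 Veterans, waves at 0, 3, 6, 9 and 12 months, within-person correlation 0.6, 40 replicates. The log-odds of loss each quarter were −2.6 − b × score. The likelihood columns use a multivariate normal model with unstructured covariance. Entries are the estimated 12-month change in SD.

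| Loss depends on | Retained | Respondent means | Paired completers | Likelihood, all waves | Likelihood, 0/3/12 only |
|---|---|---|---|---|---|
| nothing (b = 0) | 75% | 0.00 | 0.00 | 0.00 | 0.00 |
| last observed score, b = 0.5 | 73% | +0.09 | −0.01 | 0.00 | +0.01 |
| last observed score, b = 1 | 68% | +0.19 | −0.03 | 0.00 | +0.03 |
| current unobserved score, b = 1 | 68% | +0.22 | +0.03 | +0.09 | +0.09 |

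With a true decline of 0.2 SD and loss on the last observed score (b = 1, 67% retained), respondent means show 0.00, paired completers −0.23 and the all-wave likelihood model −0.20.

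Three things follow. Respondent means are the vulnerable summary. A likelihood model corrects for loss that depends on observed scores, and using all waves adds a little over three. No such model removes the bias when loss depends on scores that were never observed.

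**The case against.** The strongest reply is that the plan may already mean paired change. It speaks of change and of a pre-post analysis, which fits within-Veteran differences at least as well as a comparison of respondent means. On that reading the false gain largely goes. This stands, and it limits the point. What remains is that the text does not say which is meant, and paired results describe only Veterans still responding.

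A reader might infer that the quarterly waves are not modelled at all. The documents do not support that: the finite mixture models are joint models of each Veteran's outcomes and may use every wave. Their purpose is to find subgroups, though, not to estimate average change.

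A reader might also note the entry "GLMMs -- Generalized Linear Mixed Models" in the List of Abbreviations and conclude that such models are never used. The text available to me has a gap between section 3.0 and the data use agreements, so this cannot be established and carries no weight here.

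Finally, a reader might turn the 0.125 SD example into a test: with 1,650 at baseline and 1,237.5 at 12 months, SE = √(1/1650 + 1/1237.5) = 0.0376 and z = 3.3. The plan states no significance test for this comparison. That SE also treats overlapping respondents as independent and ignores clustering by medical center, and both the loss and the gap are assumed. The z-value should not be used.

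It is also fair to say that the documents nowhere state that leavers score worse; if they scored better, the artefact would be a false decline. Veterans not yet at 12 months are late enrollees, not a group selected on frailty.

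**Conclusion.** The point holds in limited form. Objective 1 gives no handling of Veteran attrition, does not state whether change is paired, and names no repeated-measures model for average change. Objective 2 of the same protocol recognises that Veterans will leave and plans methods for it, for Caregivers only.

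If respondent means are compared, selective loss could produce an apparent improvement of about 0.05–0.18 SD with no true change. This assumes 15–35% lost and leavers 0.3–0.5 SD worse at baseline. The frail-subgroup calculation gives 0.02–0.11 SD, and the simulation +0.09 to +0.22 SD under direct selection on the score. None of these rates or gaps comes from the documents. If change is paired, the false gain is near zero and the limitation is one of generalisability: the estimate applies to those who remain.

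**What to change.** 1. State that average change is estimated within Veteran by a likelihood-based mixed model on all available quarterly waves, with random effects for Veteran and VAMC and with baseline characteristics as covariates. Keep the descriptive means as a supplement, marked as paired or unpaired. State the waves used, and the handling of incomplete vectors, for the finite mixture models too.
2. Report baseline values by 12-month response status, separating Veterans not yet at 12 months from those who left. Give reasons for leaving where the data record them; the documents do not say that they do.
3. Extend the pattern-mixture sensitivity analysis from Objective 2 to Objective 1, since the mixed model leaves bias when loss depends on unobserved scores.
4. State that the estimate for Veterans who die needs separate interpretation, because a mixed model implicitly carries their outcomes past death.

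The cost is a few sentences of analysis text and modest extra programming. The quarterly surveys are already part of the data requested under the agreement with the Office of Geriatrics and Extended Care, so no new collection is needed. The reported improvement may turn out smaller.
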